2.2.2 Secondary Efficacy Endpoints

- Overall Survival (OS), defined as the time from randomization to death from any cause
- Two-year landmark survival, defined as survival at 2 years
- Objective response, defined as a complete response or a partial response on two consecutive occasions ≥ 4 weeks apart, as determined by the IRC according to RECIST v1.1

- Objective response, defined as a complete response or a partial response on two consecutive occasions ≥ 4 weeks apart, as determined by the investigator through use of RECIST v1.1
- PFS, defined as the time from randomization to the first occurrence of disease progression, as determined by the investigator through use of RECIST v1.1, or death from any cause, whichever occurs first
- Disease control Rate (DCR), defined as a complete response, a partial response, or stable disease at 16 weeks, as determined by the IRC through use of RECIST v1.1
- DCR, defined as a complete response, a partial response, or stable disease at 16 weeks, as determined by the investigator through the use of RECIST v1.1
- Duration of objective response, defined as the time from the first occurrence of a documented objective response to disease progression, as determined by the IRC through use of RECIST v1.1, or death from any cause, whichever occurs first
- Duration of objective response, defined as the time from the first occurrence of a documented objective response to disease progression, as determined by the investigator through use of RECIST v1.1, or death from any cause, whichever occurs first
- The change from baseline in Health-Related Quality of Life (HRQoL) scores, as assessed through use of the two-item Global Health Status/Quality of Life (GHS/QoL) subscale of the European Organization for Research and Treatment of Cancer Quality of Life Core 30 (EORTC QLQ-C30) questionnaire, at specified timepoints while receiving treatment

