2.3 DETERMINATION OF SAMPLE SIZE

Approximately 450 patients will be randomized into the study.

The overall type I error (α) for this study is 0.05 (two-sided). Formal treatment comparisons will be performed by first evaluating the primary endpoint of IRC-assessed PFS (per RECIST v1.1) at $\alpha=0.01$ (two-sided). If PFS is statistically significant at $\alpha=0.01$, then the key secondary endpoints will be evaluated at $\alpha=0.05$ (two-sided) in a hierarchical manner in the following order: OS, IRC-assessed objective response rate (ORR), and landmark OS. IRC-assessed ORR and landmark OS will be tested when OS crosses the pre-specified boundary.

The type I error (α) for the analysis of the primary endpoint of IRC-assessed PFS is 0.01 (two-sided). The analysis of the primary endpoint of IRC-assessed PFS will take place when approximately 240 PFS events have occurred. Statistical considerations are based on the following assumptions:

- Stratified log-rank test at 0.01 significance level (two-sided)
- Median PFS of 5.5 months for the pembrolizumab arm
- Median PFS of 10.0 months for the cobimetinib plus atezolizumab arm
- Enrollment period of approximately 12 months
- Annual dropout rate of 5%
- No interim analysis for PFS

A total of 240 PFS events provides approximately 98% power to detect an improvement in median PFS from 5.5 months in the pembrolizumab arm to 10.0 months in the cobimetinib plus atezolizumab arm. This corresponds to a hazard ratio (HR) of 0.55, with a minimal detectable difference of 0.72. The PFS analysis will be conducted approximately 17 months after first patient in (FPI). The final analysis of the secondary endpoint of OS will be performed after the occurrence of approximately 295 deaths. A total of 295 deaths provides approximately 60% power to detect an improvement in median OS from 28 months in the pembrolizumab arm to 37.5 months in the cobimetinib plus atezolizumab arm, corresponding to an HR of 0.75, or 80% power to detect an HR of 0.70. Two interim analyses of OS will be conducted. The final OS analysis will be conducted approximately 68 months after FPI.

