2.4 ANALYSIS TIMING

The PFS primary analysis will be conducted when approximately 240 PFS events have occurred, which is expected to occur approximately 17 months after FPI. There is no planned interim analysis for PFS.

The study will incorporate three OS analyses (two interim analyses and one final analysis). The first OS interim analysis will be performed at the time of the primary PFS analysis when a projected number of 80 deaths are expected to have occurred. The second OS interim analysis will be performed after the occurrence of approximately 153 deaths and is projected to occur at approximately 28 months after the first patient is randomized. The final OS analysis will be performed after the occurrence of approximately 295 deaths and is projected to occur approximately 68 months after the first patient is randomized. Refer to Section 4.10 for the assumptions and characteristics of the interim and final analysis for OS.

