4.4.2 Secondary Efficacy Endpoints

4.4.2.1 Overall Survival

OS is defined as the time from randomization to death from any cause. For patients who are alive at the time of analysis data cutoff, OS time will be censored at the date the patient was last known to be alive. Survival time for patients with no post-baseline survival information will be censored at randomization. The HR for OS will be estimated using a stratified Cox model, and a two-sided 95% CI for the HR will be provided. Results from an unstratified analysis will also be provided. The Kaplan-Meier approach will be used to estimate median OS and 2-year landmark survival rate. The 95% CI of the median OS will be estimated using the Brookmeyer and Crowley method ([Brookmeyer and Crowley 1982](#)). The 95% CI of landmark survival rate will be calculated using the standard error derived from Greenwood's formula ([Greenwood 1926](#)).

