4.4.2.2 Objective Response Rate by IRC and Investigator Using RECIST v1.1

Objective response rate is defined as the total number of patients whose objective response is a complete response or a partial response, divided by the number of patients in the ITT population with measurable disease at baseline. Objective response is defined as a complete response or partial response on two consecutive occasions ≥ 4

weeks apart, as determined by the IRC and or investigator using RECIST v1.1. A 95% Clopper-Pearson CI will be calculated for the ORR for each treatment arm. The difference in ORR between treatment arms will be tested using the stratified Cochrane-Mantel-Haenszel test. A 95% Hauck-Anderson CI will be calculated for the difference in ORR between treatment arms.

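### Does the formal test of 2-year landmark OS need a stated follow-up condition, given that it is tied to the OS boundary crossing?

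*SAP*

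**What the plan says.** SAP 2.3 tests IRC-assessed PFS first, at two-sided 0.01. Only if that succeeds are the key secondary endpoints tested at 0.05, "in a hierarchical manner in the following order: OS, IRC-assessed objective response rate (ORR), and landmark OS". The next sentence adds that "IRC-assessed ORR and landmark OS will be tested when OS crosses the pre-specified boundary". SAP 2.2.2 defines the endpoint: "Two-year landmark survival, defined as survival at 2 years".

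The possible crossing times follow from SAP 2.4 and Table 1 in SAP 4.10. "The first OS interim analysis will be performed at the time of the primary PFS analysis", projected at about month 17 with 80 deaths. The second interim, at about 153 deaths, "is projected to occur at approximately 28 months after the first patient is randomized". The final analysis is projected at about month 68 with 295 deaths. SAP 2.3 also assumes "Enrollment period of approximately 12 months".

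On method, SAP 4.4.2.1 says "The Kaplan-Meier approach will be used to estimate median OS and 2-year landmark survival rate", with a Greenwood confidence interval, and names no between-arm test for the landmark. For ORR, by contrast, SAP 4.4.2.2 does name one: "The difference in ORR between treatment arms will be tested using the stratified" Cochran-Mantel-Haenszel procedure. The protocol gives the same estimation methods and no testing hierarchy.

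SAP Version 3 adds, in 2.5 and 4.10, that the primary endpoint was not met, that the study ends early, and that the second interim and final OS analyses are replaced by a single OS analysis at final database lock.

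**The concern.** Read as an instruction about timing, the rule asks for a comparison of 2-year survival at whichever OS look first crosses. At month 17 the longest possible follow-up is 17 months, so a 2-year rate cannot be estimated. At month 28 it can be estimated, but from little follow-up beyond two years. Month 28 is also the look at which OS was most likely to cross first.

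Read only as a gate, the rule is workable, but the SAP does not say which data cutoff feeds the test. The cutoff would then be settled after the OS result was known. Protocol 3.3.9 presents 2-year survival as a potentially meaningful measure for patients and physicians, so a formal test without a stated cutoff or test statistic looks like a gap in pre-specification. A second worry is that the analyses after the PFS miss carry no explicit descriptive label, while Table 1 still prints OS boundaries.

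**Working it through.** **Inputs.** From SAP 2.3, 2.4 and Table 1: 450 patients, 1:1; 12-month enrolment; median OS 28 and 37.5 months; looks at months 17, 28 and 68 with 80, 153 and 295 projected deaths; OS levels 0.001, 0.040 and 0.018. The 5% annual dropout is listed with the PFS assumptions and is applied to OS here. Accrual shape is not stated. I assume that the fraction enrolled by month t is (t/12)^k, where k = 1 is uniform and k = 2 is a linear ramp-up in the enrolment rate.

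**The plan's own figures first.** Expected deaths with exponential OS and dropout:

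| k | Month 17 | Month 28 | Month 68 |
|---|---|---|---|
| 1 | 92 | 162 | 298 |
| 1.75 | 80 | 153 | 295 |
| 2 | 77 | 151 | 294 |
| SAP | 80 | 153 | 295 |

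A ramp with k near 1.75 reproduces the projections; uniform accrual does not. Three-look OS power is 60.2% at HR 0.75 and 79.6% at HR 0.70, against 60% and 80% stated.

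**When OS would first cross.** The drift of the log-rank statistic is −ln(HR)·√deaths/2.

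| HR | Month 17 | Month 28 | Month 68 |
|---|---|---|---|
| 0.75 | 2.3% | 37% | 21% |
| 0.70 | 4.5% | 52% | 23% |

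**Patients at risk at 24 months.** S(24) = exp(−ln2·24/28) = 0.552 and exp(−ln2·24/37.5) = 0.642, mean 0.597. Retention over two years is 0.95² = 0.9025. At cutoff T the number at risk is 450 × P(entry by month T−24) × 0.597 × 0.9025.

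- Month 17: T−24 is negative, so none.
- Month 28, k = 1: 450 × (4/12) = 150 enrolled early enough, 81 at risk.
- Month 28, k = 1.75: 450 × (4/12)^1.75 = 66, 35 at risk.
- Month 28, k = 2: 450 × (4/12)² = 50, 27 at risk.
- Month 36 or later: all 450, 242 at risk.

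**Precision and power.** The difference is 0.642 − 0.552 = 0.090. The Greenwood variance per arm is S(24)² × ∫ hazard/(expected number at risk) over 0 to 24 months, and power is Φ(0.090/SE − 1.96).

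| Cutoff | SE | Power |
|---|---|---|
| Month 28, k = 1 | 0.0535 | 39% |
| Month 28, k = 1.75 | 0.0611 | 31% |
| Month 28, k = 2 | 0.0645 | 28% |
| Month 36 | 0.0474 | 47% |

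The count at risk falls much more steeply than the precision does, because the Kaplan-Meier estimate uses every patient's follow-up up to 24 months.

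**Effect on the sequence.** Patient-level simulation at HR 0.75, taking ORR as passed, gives the joint chance that OS first crosses at month 28 and the landmark test succeeds. On month-28 against month-36 data it is 29% v 33% (uniform), 23% v 32% (best-fitting ramp) and 22% v 32% (linear ramp-up). The gain is 4 to 10 points before the PFS and ORR gates are counted.

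**Can the rule be triggered?** SAP 2.3 makes every key secondary test conditional on PFS. SAP 2.5 and 4.10 state that PFS failed and that the month-28 and month-68 looks will not be held as planned. The condition for the landmark test is false, so none of the differences above can affect this trial's inference.

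**The case for a change.** The strongest contrary case is that a formally tested endpoint had neither a cutoff nor a named test, and that the gap was cheap to close. A single test at 0.05, behind the gate, once the last patient has 24 months of potential follow-up would spend no extra alpha. Given a first crossing at month 28 with HR 0.75, it would raise the chance of landmark success from 79% (uniform) or 62% (linear ramp-up) to 89% or 87%. As a criticism of the drafting, that stands. It is weaker than it looks for three reasons.

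- The sentence closes a paragraph on testing order, where crossing the boundary reads naturally as opening a gate. A statistician meeting a month-17 crossing would wait for 2-year data.
- The Kaplan-Meier rates and Greenwood standard errors in SAP 4.4.2.1 already supply the usual test of the difference.
- The claim that no further follow-up is needed assumes that survival follow-up would continue after an interim crossing. No section says so.

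Two further points remain. An explicit descriptive label in SAP 2.5 and 4.10 would be tidy, but SAP 2.3 already rules out formal secondary testing after a PFS miss, and both later sections say that the OS looks are not held as specified. Giving OS its own alpha after a PFS miss is a design preference. Protocol 3.3.9 gives the sponsor's reason for putting PFS first, and alpha cannot be reassigned after the PFS readout.

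**Conclusion.** The observation about the text is correct, but no change follows. As drafted, the rule could not have been carried out literally at month 17 (a 2–5% chance of arising) and would have given a less precise, still estimable, comparison at month 28: power 28–39% against 47% at month 36, or about 31% under the accrual shape that fits the SAP's projected deaths. These figures rest on exponential survival, 5% annual dropout applied to OS, and an assumed accrual shape. In SAP Version 3 the hierarchy is closed by the PFS miss, so a cutoff and a named test would alter no analysis and no conclusion. What is left is an unstated descriptive label, which a reader can infer from SAP 2.3 and which analysts would supply when reporting nominal 95% intervals.

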2.4 ANALYSIS TIMING

The PFS primary analysis will be conducted when approximately 240 PFS events have occurred, which is expected to occur approximately 17 months after FPI. There is no planned interim analysis for PFS.

The study will incorporate three OS analyses (two interim analyses and one final analysis). The first OS interim analysis will be performed at the time of the primary PFS analysis when a projected number of 80 deaths are expected to have occurred. The second OS interim analysis will be performed after the occurrence of approximately 153 deaths and is projected to occur at approximately 28 months after the first patient is randomized. The final OS analysis will be performed after the occurrence of approximately 295 deaths and is projected to occur approximately 68 months after the first patient is randomized. Refer to Section 4.10 for the assumptions and characteristics of the interim and final analysis for OS.

2.5 PREMATURE TERMINATION OF STUDY AFTER PRIMARY ANALYSIS

Given that the study did not meet the primary endpoint and did not demonstrate a benefit of cobimetinib plus atezolizumab vs. pembrolizumab, it will be terminated early. Therefore, the second interim and final OS analyses will not be conducted as specified elsewhere in this document. Instead, a final OS analysis will be conducted at the time of final database lock.

3. STUDY CONDUCT

3.1 RANDOMIZATION ISSUES

Randomization to the two treatment arms will occur in a 1:1 ratio. A permuted-block randomization will be applied to ensure a balanced assignment to each treatment arm. Randomization and stratification will be managed through an IWRS. Randomization will be stratified by the following factors:

- PD-L1 status (IC0 vs. IC1, 2, 3)
- Baseline serum LDH level (less than or equal to the ULN vs. greater than the ULN)
- Geographic region (North America vs. Europe vs. Australia, New Zealand, and others).

3.2 INDEPENDENT REVIEW FACILITY

An IRC will be used for this study. PFS based on blinded independent review assessments is the primary endpoint for this study. ORR, DCR, and DOR based on blinded independent review assessments are secondary endpoints. For details about the IRC, refer to the IRC Charter.

3.3 DATA MONITORING

An independent Data Monitoring Committee (iDMC) is used to conduct periodic evaluations of safety data. All analyses for the iDMC's review will be prepared by an independent Data Coordinating Center (iDCC). For details about the iDMC, refer to the iDMC Charter.

4. STATISTICAL METHODS

The analyses described in this SAP will supersede those specified in Protocol CO39722 for the purpose of a regulatory filing.

4.1 ANALYSIS POPULATIONS

4.1.1 Randomized Population

The randomized population or intent-to-treat (ITT) population is defined as all randomized patients, whether or not the patient received the assigned treatment.

4.1.2 Pharmacokinetic-Evaluable Population

The pharmacokinetic (PK) -evaluable population is defined as all patients who have received at least one dose of study drug and for whom at least one evaluable PK sample is collected.

4.1.3 Immunogenicity-Evaluable Population

The baseline ADA-evaluable population for each study treatment includes patients who had a baseline ADA result. The post-baseline ADA-evaluable population for each study treatment includes patients who had at least one post-baseline ADA result and had received at least one dose of that study treatment.

4.1.4 Safety Population

The safety population is defined as all patients who received at least one dose of study drug, with patients grouped according to treatment received as follows:

- Cobimetinib + atezolizumab arm (Arm A): patients who received any amount of cobimetinib or atezolizumab
- Pembrolizumab arm (Arm B): patients who received any amount of pembrolizumab without any amount of either atezolizumab or cobimetinib.

4.2 ANALYSIS OF STUDY CONDUCT

Study enrollment, major protocol deviations including major deviations of inclusion/exclusion criteria, and reasons for study discontinuation will be summarized overall and by treatment arm for the ITT population. Study treatment administration and reasons for discontinuation from study treatment will be summarized for the safety population.

4.3 ANALYSIS OF TREATMENT GROUP COMPARABILITY

Demographic characteristics, such as age, race/ethnicity, baseline disease characteristics (e.g., Eastern Cooperative Oncology Group [ECOG] performance status), and stratification factors will be summarized by treatment arm for the ITT population. Descriptive statistics (mean, median, standard deviation [SD], and range) will be presented for continuous data, and frequencies and percentages will be presented for categorical data.

4.4 EFFICACY ANALYSIS

Unless otherwise noted, efficacy analyses will include all randomized patients, and patients will be grouped according to the treatment assigned at randomization. The stratification factors will be those used for randomization and will be obtained from the IWRS (PD-L1 status, baseline serum LDH level and geographic region). Due to the potential risk of over-stratification ([Akazawa et al. 1997](#)), if at least one stratum (i.e., a combination of stratification factor levels across PD-L1 status, baseline serum LDH level and geographic region) has fewer than 10 IRC-assessed PFS events across treatment arms, the stratification factor (one of three stratification factors: PD-L1 status, baseline

serum LDH level and geographic region per IWRS) which contains the level with the smallest number of patients will be removed from the stratified analyses. The removal of the stratification factors will continue until there is no stratum with fewer than 10 IRC-assessed PFS events. The final set of stratification factors used in stratified analyses will be applied to all endpoints where stratified analyses are planned.

4.4.1 Primary Efficacy Endpoint

The primary efficacy analysis will be the comparison of PFS, as determined by the IRC, between the two treatment arms using the stratified log-rank test at an overall 0.01 significance level (two-sided).

PFS is defined as the time from randomization to the first occurrence of disease progression, as determined by the IRC according to RECIST v1.1, or death from any cause, whichever occurs first. Data for patients who have not experienced disease progression or death will be censored at the last tumor assessment date. Data for patients with no post-baseline tumor assessment will be censored at randomization.

The HR for PFS will be estimated using a stratified Cox model and two-sided 95% CIs for the HR will be provided. Results from an unstratified analysis will also be provided. Kaplan-Meier methodology will be used to estimate the median PFS for each treatment arm, and Kaplan-Meier curves will be produced. The 95% CI of the median PFS for each treatment arm will be constructed using the Brookmeyer and Crowley method ([Brookmeyer and Crowley 1982](#)).

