4.4.5 Sensitivity Analyses

The impact of missed scheduled tumor assessments on IRC-assessed PFS will be assessed depending on the number of patients who missed assessments. If > 5% of patients missed two or more assessments scheduled immediately prior to the date of disease progression per RECIST v1.1 or death, a sensitivity analysis will be performed where patients who missed two or more scheduled assessments immediately prior to the date of disease progression per RECIST v1.1 or death will be censored at the last tumor assessment prior to the missed visits.

A sensitivity analysis will also be conducted on IRC-assessed PFS to determine the impact of non-protocol anti-cancer therapy. Patients who die or progress after having received non-protocol anti-cancer therapy will be censored at the date of the last evaluable tumor assessment prior to start of non-protocol anti-cancer therapy.

If more than 5% of patients have central results that indicate their tumors are BRAF mutation positive, then a sensitivity analysis will be conducted on IRC-assessed PFS with these patients excluded.

Statistical methodologies analogous to those used in the analysis of PFS as specified in Section 4.4.1 will be used for these sensitivity analyses.

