If prior to enrollment it is known that a patient is unable to undergo CT scans with intravenous (IV) contrast because of allergy or renal insufficiency, the decision as to whether a non-contrast CT or MRI (without IV contrast) will be used to evaluate the patient at baseline and during the study should be guided by the tumor type under investigation and the anatomic location of the disease. For patients who develop contraindications to contrast after baseline contrast CT is done, the decision as to whether non-contrast CT or MRI (enhanced or non-enhanced) will be performed should also be based on the tumor type and the anatomic location of the disease, and should be optimized to allow for comparison with the prior studies if possible. Each case should be discussed with the radiologist to determine if substitution of these other approaches is possible and, if not, the patient should be considered not evaluable from that point forward. Care must be taken in measurement of target lesions and interpretation of non-target disease or new lesions on a different modality, since the same lesion may appear to have a different size using a new modality.

ENDOSCOPY, LAPAROSCOPY, ULTRASOUND, TUMOR MARKERS, CYTOLOGY, HISTOLOGY

Endoscopy, laparoscopy, ultrasound, tumor markers, cytology, and histology cannot be utilized for objective tumor evaluation.

ASSESSMENT OF TUMOR BURDEN

To assess objective response or future progression, it is necessary to estimate the overall tumor burden at baseline and use this as a comparator for subsequent measurements.

IDENTIFICATION OF TARGET AND NON-TARGET LESIONS

When more than one measurable lesion is present at baseline, all lesions up to a maximum of five lesions total (and a maximum of two lesions per organ) representative of all involved organs should be identified as target lesions and will be recorded and measured at baseline. This means that, for instances in which patients have only one or two organ sites involved, a maximum of two lesions (one site) and four lesions (two sites), respectively, will be recorded. Other lesions (albeit measurable) in those organs will be considered non-target lesions.

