Any	Any	Yes	PD

CR=complete response; NE=not evaluable; PD=progressive disease; PR=partial response; SD=stable disease.

MISSING ASSESSMENTS AND NOT-EVALUABLE DESIGNATION

When no imaging/measurement is done at all at a particular timepoint, the patient is not evaluable at that timepoint. If measurements are made on only a subset of target lesions at a timepoint, usually the case is also considered not evaluable at that timepoint, unless a convincing argument can be made that the contribution of the individual missing lesions would not change the assigned timepoint response. This would be most likely to happen in the case of PD. For example, if a patient had a baseline sum of 50 mm with three measured lesions and during the study only two lesions were assessed, but those gave a sum of 80 mm, the patient will have achieved PD status, regardless of the contribution of the missing lesion.

SPECIAL NOTES ON RESPONSE ASSESSMENT

Patients with a global deterioration in health status requiring discontinuation of treatment without objective evidence of disease progression at that time should be reported as "symptomatic deterioration." Every effort should be made to document objective progression even after discontinuation of treatment. Symptomatic deterioration is not a descriptor of an objective response; it is a reason for stopping study therapy. The objective response status of such patients is to be determined by evaluation of target and non-target lesions as shown in [Table 1](#).

For equivocal findings of progression (e.g., very small and uncertain new lesions; cystic changes or necrosis in existing lesions), treatment may continue until the next scheduled assessment. If at the next scheduled assessment, progression is confirmed, the date of progression should be the earlier date when progression was suspected.

REFERENCE

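### Primary PFS is censored at the last tumor assessment without requiring that it be evaluable, so event-free patients with terminal not-evaluable scans are counted as progression-free for too long

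*SAP*

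**What the plan says.** **Primary rule.** SAP 4.4.1 and protocol 6.4.1 use the same words: "Data for patients who have not experienced disease progression or death will be censored at the last tumor assessment date". Patients without any post-baseline assessment are censored at randomization. SAP 4.9 (Missing Data) only points back to 4.4.1 and 4.4.2. Investigator PFS (SAP 4.4.2.3) and duration of response (SAP 4.4.2.5) take over the same censoring method.

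**Not-evaluable timepoints.** SAP Appendix 4 (RECIST v1.1; protocol Appendix 3) creates them in two ways. If contrast becomes contraindicated and no substitute technique is possible, "the patient should be considered not evaluable from that point forward". If only some target lesions are measured, "usually the case is also considered not evaluable at that timepoint". NE is a formal overall-response category in Table 1 of that appendix. Under protocol 4.5.5, scheduled scans continue until progression, including in patients who stop treatment for other reasons.

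**Sensitivity runs.** In SAP 4.4.5, patients who progress or die after starting other anti-cancer treatment are "censored at the date of the last evaluable tumor assessment prior to start of non-protocol anti-cancer therapy". The missed-assessment run in the same section goes back to the last assessment before the missed visits and does not mention evaluability.

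**The concern.** A scan that took place but was judged NE is still, on the plain wording, a tumor assessment with a date. An event-free patient whose last scans are NE is therefore censored at the last of them. The interval since the last evaluable scan enters the risk set as progression-free time, although progression in the target lesions could not be fully assessed during it.

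The fallback has the same gap. A patient whose post-baseline scans are all NE did have assessments, so is censored at the last NE scan and not at randomization.

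The extra time lowers the estimated event rate in the arm that contains it. If NE is more frequent in one arm, the hazard ratio moves in that arm's favour. The same applies to investigator PFS, and duration of response is lengthened in the same way.

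**Working it through.** **1. The plan's own figures.** SAP 2.3 gives "Stratified log-rank test at 0.01 significance level (two-sided", "Median PFS of 5.5 months for the pembrolizumab arm" and "Median PFS of 10.0 months for the cobimetinib plus atezolizumab arm", with 240 events and about 98% power. "This corresponds to a hazard ratio (HR) of 0.55, with a minimal detectable difference of 0.72".

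- Hazard ratio: 5.5 / 10.0 = 0.55.
- Power (Schoenfeld, 1:1): Φ(√240/2 × |ln 0.55| − 2.576) = Φ(7.746 × 0.598 − 2.576) = Φ(2.06) = 0.980.
- Minimal detectable difference: exp(−2 × 2.576 / √240) = 0.717, which rounds to 0.72.

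Both reproduce. The point disputes neither, and the fix does not change the formula inputs.

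**2. A literal case.** Take stable disease at Weeks 8 and 16, NE at Weeks 24 and 32, then data cutoff with no event. As written, the patient is censored at Week 32. Under last-evaluable censoring it is Week 16. The difference is 16 weeks, or 16 / 4.345 = 3.7 months, against a planned control median of 5.5 months.

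**3. Do the planned sensitivity runs catch it?** No. Both censoring runs in SAP 4.4.5 re-date patients who progressed or died. An event-free patient with NE scans keeps the 4.4.1 date in both. The missed-assessment run also requires missed visits, and these visits took place.

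**4. Size when NE is permanent.** The documents give no NE rate, so the rates below are assumptions.

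Set-up A: 225 patients per arm, true median 5.5 months in both arms (true hazard ratio 1.00), uniform 12-month accrual, cutoff at month 17, 8-weekly scans, 1,500 replicates. NE onset is drawn at random over all scheduled scans, independently of progression. Scans continue but show no progression after onset.

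Set-up B: onset at scans 1 to 4, 5% annual dropout, 2,000 runs, without deaths or with deaths as 10% of first events.

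| Set-up | NE, Arm A / Arm B | Deaths | HR as written | HR, last evaluable |
|---|---|---|---|---|
| A | 2% / 0% | none | 0.983 | 0.997 |
| A | 5% / 0% | none | 0.965 | 1.000 |
| A | 5% / 0% | planned 28-month median OS | 0.975 | about 1.00 |
| B | 2% / 0% | none; 10% | 0.982; 0.988 | 1.00 |
| B | 5% / 0% | none; 10% | 0.954; 0.967 | 1.00 |
| B | 5% / 5% | none; 10% | about 1.00 | about 1.00 |

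In set-up A at 5% / 0% without deaths, favourable results at two-sided p<0.01 occur in 1.6% of trials as written, against a nominal 0.5% in that direction.

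**5. Size when only the last k scans are NE.** This uses 450 patients, 5% annual dropout, cutoff at month 17, no separate deaths and 2,000 runs.

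| True HR | NE, Arm A / Arm B | k | HR as written | HR, last evaluable |
|---|---|---|---|---|
| 1.00 | 5% / 5% | 1 | 0.998 | 0.998 |
| 1.00 | 10% / 5% | 2 | 0.985 | 1.000 |
| 1.00 | 20% / 5% | 2 | 0.953 | 0.999 |
| 1.00 | 5% / 10% | 2 | 1.013 | 0.997 |
| 0.55 | 10% / 5% | 2 | 0.571 | 0.580 |

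With a true hazard ratio of 0.55 and no NE, this set-up returns 0.577 because events are dated on the 8-week grid. That is the reference for the last row.

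All these runs are unstratified, use a fixed month-17 cutoff instead of stopping at 240 events, and treat NE as uninformative. They also let no progression be detected at an NE scan, which overstates the effect for the reason given under the objection.

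**The case against.** **NE is not blind.** A reader might infer that an NE patient cannot have a radiographic event. Table 1 of the RECIST appendix says otherwise: any new lesion is progression, unequivocal non-target progression is progression, and the appendix allows progression to be called from a subset of target lesions. Death also remains an event. This stands, and it limits the harm to progression that would have shown only in the unmeasured target lesions.

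**A larger figure is tempting.** A 5% versus 0% imbalance can be made to give a hazard ratio near 0.92 to 0.93, but only by drawing NE onset at or before the scan that would have shown progression, so that every affected patient loses the event. Nothing in the documents supports that dependence. With onset over all scheduled scans the effect is about half as large.

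**The imbalance is assumed.** The scan schedule is identical in both arms (protocol 4.5.5), and balanced NE leaves the hazard ratio unchanged. This stands. A difference between arms is possible but not shown.

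**The rule may be settled elsewhere.** No text says outright that NE scans count; the rule is silent. SAP 3.2 refers to an IRC Charter that is not among the documents and may define this. Nor can last-evaluable censoring be called the SAP's general standard, since only one of its two censoring runs uses it.

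**Timing.** SAP version 3 (section 2.5) reports that the primary endpoint was not met. Rewriting the primary rule now and re-running it as primary would be a post hoc change. This stands and shapes the fix.

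None of this removes the gap in the wording or the inconsistency within SAP 4.4.5.

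**Conclusion.** The point holds as a defect in the stated censoring rule. Followed literally, the rule counts time with unestablished status as progression-free time, the all-NE patient has no route back to randomization, and no planned run corrects either.

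The likely effect is small. Under assumed permanent NE of 5% versus 0%, with onset independent of progression, a true hazard ratio of 1.00 becomes about 0.97, or 0.975 with deaths at the planned 28-month median OS. At 2% versus 0% it is about 0.98 to 0.99, and with balanced NE it is unchanged. The arm with more NE scans is favoured.

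Two stronger conclusions are not supported. The documents do not show that the reported primary result was biased, because they give neither NE counts nor the Charter's handling. They also do not show that the SAP deliberately counts NE scans as evidence of no progression.

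**What to change.** In SAP 4.4.1 and protocol 6.4.1, censor event-free patients at the date of the last evaluable assessment, meaning an overall response other than NE by the same assessor (IRC or investigator). Censor at randomization if there is no evaluable post-baseline assessment. Investigator PFS and duration of response inherit the rule. Use the same term in both censoring runs of SAP 4.4.5.

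If the IRC Charter already works this way, say so in the SAP; nothing else is then needed for the IRC endpoints.

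Because the primary analysis was done under the existing text, keep it as the primary result. Report the re-run as a labelled sensitivity analysis, with the number of event-free patients by arm whose final scans were NE. If those counts are low and similar, the matter is closed.

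The cost is one phrase, one filter on the overall-response variable and one small table. The downside is that a few censoring dates move earlier.
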